1.3 Exploratory Objectives

- 1.3.1 To measure the absolute lymphocyte count (ALC) prior to treatment and during treatment. We will compare changes in ALC between responders and non-responders given evidence that ALC after two cycles may be a predictor of clinical response in solid tumors.
- 1.3.2 To evaluate the genome for evidence of clonal evolution among longitudinal samples (prior to treatment, during treatment, and at relapse if relevant) from individual patients. We will compare leukemic genotypic patterns among responders and non-responders.
- 1.3.3 To evaluate the histopathologic findings of immune response using immunohistochemistry.
- 1.3.4 To determine the immune response in the AML tumor microenvironment by using flow cytometry and single cell mass cytometry to evaluate T cell subsets. We will evaluate cytokine and chemokine panels. We will further evaluate the gene expression patterns of immune infiltrates. We will evaluate for alterations in antigen presenting cells in response to decitabine and combination therapy. We will evaluate for resistance to immune response due to STAT3 activation.

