In addition, in all ipilimumab trials examined to date, mean Absolute Lymphocyte Count (ALC) increased after ipilimumab treatment throughout the 12-week induction-dosing period, in a dose-dependent manner. In an analysis of ipilimumab at 0.3, 3, or 10 mg/kg in melanoma studies CA184007, CA184008, and CA184022 combined, the rate of change in ALC after ipilimumab treatment was significantly associated with dose ($p = 0.0003$), with the largest rate at 10 mg/kg ipilimumab. Moreover, the rate of change in ALC over the first half of the induction-dosing period was significantly associated with clinical activity in these studies ($p = 0.009$), where clinical activity was defined as CR, PR, or prolonged SD (i.e., SD lasting at least 6 months from first dose). Although these analyses alone could not determine whether the rate of change in ALC was specifically associated with clinical activity in response to ipilimumab treatment, as opposed to being generally prognostic, these results do suggest a potential benefit to higher rates of ALC increase after ipilimumab treatment. Among the 3 doses evaluated, 10 mg/kg ipilimumab led to the greatest such rates.

In the 3 primary studies conducted in advanced melanoma (CA184007, CA184008, and CA184022), subjects treated with 10 mg/kg single agent ipilimumab had the highest response, disease control rates, median OS as well as 1-year and 2-year survival rates compared to lower doses. The CA184022 data are summarized in the table below.

Summary of Phase 2 Response Data in Melanoma (CA184022 see IB)

	10 mg/kg (n = 72)	3 mg/kg (n = 72)	0.3 mg/kg (n = 73)
BORR (mWHO) - %	11.1	4.2	0
(95% CI)	(4.9 - 20.7)	(0.9 - 11.7)	(0.0 - 4.9)
DCR (mWHO) - %	29.2	26.4	13.7
(95% CI)	(19.0 - 41.1)	(16.7 - 38.1)	(6.8 - 23.8)
Survival rate at 1 year - %	48.64	39.32	39.58
%, 95% CI	(36.84, 60.36)	(27.97, 50.87)	(28.20, 51.19)
Survival rate at 2 year - %	29.81	24.20	18.43
%, 95% CI	(19.13, 41.14)	(14.42, 34.75)	(9.62, 28.22)
Overall median survival	11.43	8.74	8.57
95%CI (months)	(6.90, 16.10)	(6.87, 12.12)	(7.69, 12.71)

Dose, Schedule, and Regimen

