9.4 Pharmacodynamic Study

Objective #1: Measuring absolute lymphocyte count as a potential biomarker for response to ipilimumab. We will compare measured levels at baseline (defined as prior to dosing on cycle 1 day 1) and at pre-determined time points (end of cycles 1, 2, and 4) and we will also compare changes in ALC from baseline (defined as prior to dosing on cycle 1 day 1) to the pre-determined time point (end of cycle 2) for survival differences given the evidence that ALC after two cycles may be a predictor of clinical response. As decitabine may cause myelosuppression, ALC elevation may not be reliable. We will compare measured levels at baseline (defined as prior to dosing on cycle 1 day 1) and at pre-determined time points (end of cycles 1, 2, and 4) and we will also compare changes in ALC from baseline (defined as prior to dosing on cycle 1 day 1) to the pre-determined time point (end of cycle 2) for survival differences given the evidence that ALC after two cycles may be a predictor of clinical response.

-Time-points: baseline, end of cycles 1, 2, and 4

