13.5 Analysis of Secondary Endpoints

Safety analyses will be based on the safety population, defined as all enrolled patients receiving at least 1 dose of ipilimumab. Categorical data will be presented as frequencies and percentages. All tests of treatment effects will be conducted at a 2-sided alpha level of 0.05, unless otherwise stated. All tests of interactions will be conducted at a 2-sided alpha level of 0.1, and all CIs will be given at a 2-sided 95% level, unless otherwise stated. Patients who are registered to the study and have received at least one dose of ipilimumab on study will be evaluable for response.

Clinical response to treatment will be assessed following the 2003 IWG criteria for AML [6] and the 2006 IWG criteria for MDS [7]. Anti-leukemic activity will be described in terms of best overall response rate (for AML, to include CR+CRi; for MDS, to include CR+marrow CR+PR+HI), PFS, OS, and remission duration. Time to event summaries will use the Kaplan-Meier method. We will separately evaluate the incidence of acute GVHD and chronic GVHD in patients in the post-allo-HCT cohort, and compare these events with response to treatment.

The focus of this trial is to establish the safety and RP2D of the combination; thus the biomarker studies should be considered exploratory. We will evaluate whether or not absolute lymphocyte count can predict for response for patients who receive combination treatment. ALC levels will be divided into: low (<1000 cells/ul) and normal/high (greater than or equal to 1000 cells/ul). We will compare the response and overall survival of patients with low ALC versus normal/high ALC using Kaplan-Meier estimates and differences will be assessed using log-rank test. We will further capture the absolute change in ALC level measured at baseline to end of cycle 2 (collected prior to dosing on cycle 3 day 1) for response and survival differences. For correlative laboratory tests, we will compare nonrandom measurements in an individual patient either across time (pre-treatment versus on-treatment) with a paired Student *t* test. OS will be censored at the date of last contacts.

REFERENCES

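### Section 13.5 splits lymphocyte count at 1000 cells/ul with no stated basis and applies log-rank to a response rate; a continuous analysis would be a cheap, low-severity improvement

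*Combined protocol and SAP*

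**What the plan says.** Section 13.5 (Analysis of Secondary Endpoints) sets the cut: "ALC levels will be divided into: low (<1000 cells/ul) and normal/high (greater than or equal to 1000 cells/ul". Response and OS are then compared between the two groups "using Kaplan-Meier estimates and differences will be assessed using log-rank test". Sections 13.1 and 13.5 define response as a best overall response rate (CR+CRi for AML; CR, marrow CR, PR and HI for MDS).

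The same paragraph says "thus the biomarker studies should be considered exploratory", and adds a second ALC analysis without a cut: "We will further capture the absolute change in ALC level measured at baseline to end of cycle 2", to be examined against response and survival. That sentence names no test.

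Other relevant text:
- Section 1.3.1 states the objective in terms of change: "We will compare changes in ALC between responders and non-responders".
- Sections 2.5 and 9.4 define baseline ALC as the value before dosing on cycle 1 day 1, which follows the decitabine lead-in. Section 9.4 warns: "As decitabine may cause myelosuppression, ALC elevation may not be reliable".
- Sections 11.1.2 and 13.1 count OS from registration.
- Section 13.2 caps enrolment at 24 per arm, 48 in total.

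Section 13.5 does not say which ALC time point is split.

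**The concern.** ALC is a continuous count. After the split, patients at 990 and 1010 are treated as different, and patients at 200 and 990 as the same. If the relation between ALC and outcome is graded, this discards information that a trial of at most 48 patients can ill afford.

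The background in Section 2.2.1 is at least compatible with a graded relation. In the melanoma studies, "the rate of change in ALC over the first half of the induction-dosing period was significantly associated with clinical activity". Nothing in the documents proposes a threshold at 1000 cells/ul.

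Two details of the same sentence add to the problem. A response rate is not a time-to-event outcome, so log-rank does not fit it without a time-to-response definition, which the plan does not give. And an ALC taken at cycle 1 day 1 or later, related to OS from registration, gives every patient with a value a stretch of follow-up in which death could not occur.

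At stake is the sensitivity of one exploratory biomarker question.

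**Working it through.** **No stated figure to reproduce.** The documents give no power, effect size, event count or ALC distribution for this analysis. Everything below except the maximum of 48 patients is an assumption or follows from one. The two-sided 0.05 level is stated in Section 13.5 for treatment effects ("All tests of treatment effects will be conducted at a 2-sided alpha level of 0.05") and is assumed to carry over.

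**Step 1: information kept by the cut.** For a normal covariate with a linear effect, split at quantile q, relative efficiency is φ(z_q)² / [q(1−q)].
- q = 0.5: 0.3989² / 0.25 = 0.64
- q = 0.7 (or 0.3): 0.3477² / 0.21 = 0.58
- q = 0.8 (or 0.2): 0.2800² / 0.16 = 0.49

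In patient terms, of 48 this resembles setting aside 48 × 0.36 ≈ 17 at a median split and 48 × 0.51 ≈ 24 at 80/20. It does not depend on the effect size.

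**Step 2: power by formula.** Non-centrality is √D × |ln HR per SD|, multiplied by the square root of the efficiency when ALC is cut. With D = 25 deaths and HR 0.6:
- continuous: 5 × 0.511 = 2.55, power Φ(2.55 − 1.96) = Φ(0.59) ≈ 72%
- median cut: 2.55 × 0.798 = 2.04, power Φ(0.08) ≈ 53%

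**Step 3: power by simulation (OS, 48 patients).** A Cox score test on continuous log ALC is set against log-rank on the split.
- About 25 deaths: exponential survival, 49% alive at 12 months, follow-up stopped at 12 months. The 49% is borrowed from the post-transplant ipilimumab study in Section 2.4.
- About 41 deaths: median survival 7 months, censoring uniform over 12 to 36 months. The median is assumed, near the 7.7 months quoted in Section 2.1 for untreated elderly AML.

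| Deaths | HR per SD | Continuous | Cut, 50% below 1000 | Cut, 70% below | Cut, 80% below |
|---|---|---|---|---|---|
| 25 | 0.6 | 69% | 49% | 36% | 26% |
| 25 | 0.7 | 42% | 28% | 21% | 16% |
| 41 | 0.6 | 86% | 66% | 55% | 46% |

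The extremes over HR 0.5 to 0.7, 25 to 41 deaths and 30% to 80% of patients below the cut both occur at HR 0.5:
- 90% against 42%, a loss of 48 points (25 deaths, 80% below)
- 98% against 88%, a loss of 10 points (41 deaths, 30% below)

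Simulated losses at 80/20 exceed those from the formula because the small high-ALC group then has few deaths. With no true effect, both tests reject about 5% to 6% of the time.

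**Step 4: response (48 patients, assumed rate 25%).** With an odds ratio of 2.5 per SD, power is about 73% continuous against 54% at a median split, and 72% against 41% if 30% are below 1000. Over odds ratios 1.5 to 3 the loss is 4 to 33 points.

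**Step 5: the opposite case.** If the true effect is a step exactly at 1000 (HR 2 to 3 between the groups, 48 patients), the cut gains 11 to 28 points. For example, at HR 2.5 with equal groups it has 77% power against 56%.

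**The case against.** The strongest reply is that this is one exploratory analysis with a cut fixed in advance. That is correct: the type I error is not inflated and dose selection does not depend on ALC. The plan already warns that ALC may be unreliable on decitabine. It also has an uncut analysis of change, which is the one that serves objective 1.3.1. This limits the severity. It does not repair the level analysis, which asks a different question.

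Second, small numbers cause much of the risk of a miss. At HR 0.7 and 25 deaths the continuous test also misses 58% of the time, and in one arm of 24 at HR 0.6 it misses 60%. With about 41 deaths, HR 1.75 to 2.0 per SD and a near-median cut, the split still has about 73% to 87% power. Section 5.6 follows patients for up to a year after removal from study, so 25 deaths may be too few. More deaths reduce the miss risk but leave a loss.

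Third, several stronger readings are tempting and the documents do not support them:
- That the plan loses some fixed number of power points. The inputs for such a figure are not in the documents.
- That most patients will fall below 1000. Lymphopenia after the lead-in is plausible, but no distribution is given.
- That a false negative is likely and would drop ALC from phase 2. No rule turns a non-significant result into that conclusion; Sections 1 and 2.4 tie further testing to safety, tolerability and preliminary efficacy.
- That the cited melanoma work proves a continuous model right. Section 2.2.1 reports an association with rate of change but not how it was modelled.

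**Conclusion.** The point holds as a low-severity improvement. Section 13.5 splits a continuous count at 1000 cells/ul without a stated basis and names a survival method for a response rate. If log ALC is normal and its effect on the log hazard is linear, the split keeps about 64% of the information at a median split and about 49% at 80/20. The OS power loss at 48 patients is then roughly 10 to 48 points over the range in Step 3. That range is driven by assumptions, and the sign reverses for a step at 1000. The consequence is a higher chance of missing a real association in an exploratory analysis. The MTD/RP2D and the type I error are unaffected.

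**What to change.** Rewrite the ALC level sentences in Section 13.5:
- **OS:** a Cox model on log(ALC), stratified by arm, reporting the hazard ratio per doubling with its confidence interval. Count OS from the ALC measurement: cycle 1 day 1 for the baseline value, and a landmark for any on-treatment value. Name the time point.
- **Response:** compare ALC between responders and non-responders by rank-sum, or use logistic regression on log(ALC). Drop Kaplan-Meier and log-rank for response.
- **The 1000 cells/ul groups:** keep them only for a descriptive Kaplan-Meier plot of OS.

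The cost is one paragraph of statistical text. ALC is already collected, so no new data or patients are needed. The downside is an assumption of log-linearity, which at most 48 patients can test only crudely.

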While optimal doses and schedules for ipilimumab have not yet been determined, in proposed proof of principle studies demonstration of efficacy at 10 mg/kg would allow future studies to explore biologic and clinical efficacy at lower doses with reduced toxicity. For most studies in new combinations or settings, a short phase 1 component at 3 mg would be appropriate with a 5 or 6 mg/kg dose added as an additional cohort if needed.

A recommended dose of 10 mg/kg is proposed by the manufacturer for most studies of ipilimumab. In melanoma, a similar survival benefit was demonstrated in phase 3 trials at the 3 mg/kg and at 10 mg/kg with DTIC. However, the incidence of grade ≥ 3 toxicity was 15 and 25% respectively.

Based on Phase 2 studies, response rates of ipilimumab appear to be dose dependent up to 10 mg/kg. Exposure-response analyses [C_{minSS} Analysis of PK data from patients treated with ipilimumab at 0.3 mg/kg (N=47), 3 mg/kg (N=60) and 10 mg/kg (N=311)], showed that the target C_{minSS} target threshold of 20 mcg/ml was exceeded in 0%, 30% and 95% subjects respectively. The slope of change in absolute lymphocyte count (ALC) correlated with clinical benefit and T-cell activation markers such as HLA-class II expression may also be dose dependent. Responses have not been compared systematically in randomized phase 2 or phase 3 studies in patients with tumor types other than melanoma.

Regarding schedule, the typical schedule for advanced melanoma at present is once q3w for four doses followed by a maintenance phase of four doses every 12 weeks. Of interest, ipilimumab was evaluated in NSCLC and SCLC using a dose of 10 mg/kg given concomitantly or following initial paclitaxel/cisplatin. When used in the phased schedule, 10 mg significantly improved irPFS and mWHO defined responses but not PFS determined by Response Evaluation Criteria in Solid Tumors (RECIST). There also was a trend for an improvement in OS in both indications. Doses less than 10 mg/kg have not been evaluated in either NSCLC or SCLC.

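### Section 13.5 names no adjustment for ipilimumab dose in the ALC analyses, so dose alone could produce or inflate an association between on-treatment ALC and outcome

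*Combined protocol and SAP*

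**What the plan says.** Section 13.5 asks whether ALC predicts outcome in patients who receive the combination. It sets one cut-point: "ALC levels will be divided into: low (<1000 cells/ul) and normal/high (greater than or equal to 1000 cells/ul"). It then states: "We will compare the response and overall survival of patients with low ALC versus normal/high ALC using Kaplan-Meier estimates", with differences assessed by log-rank test. The next step is: "We will further capture the absolute change in ALC level measured at baseline to end of cycle 2", again in relation to response and survival. No stratum or covariate is named for either analysis, and section 13.3 (Stratification Factors) has a heading but no content.

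Section 13.5 does not say when the dichotomised ALC is measured. Section 9.4 lists "baseline (defined as prior to dosing on cycle 1 day 1) and at pre-determined time points (end of cycles 1, 2, and 4") and adds that "we will also compare changes in ALC from baseline" to the end of cycle 2. Exploratory objective 1.3.1 sets ALC changes in responders against those in non-responders.

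Section 13.1 treats efficacy differently. Response is assessed in patients at the MTD/RP2D of each arm, and OS and PFS within each arm. Section 13.5 does not repeat these limits for ALC.

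On dose, section 2.2.1 reports for melanoma that "the rate of change in ALC after ipilimumab treatment was significantly associated with dose" (p = 0.0003, largest rate at 10 mg/kg), and that "response rates of ipilimumab appear to be dose dependent up to 10 mg/kg". Section 2.4 reports no formal response at 3 mg/kg (6 evaluable patients) and 7/22 at 10 mg/kg in the earlier post-transplant ipilimumab study.

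**The concern.** Each arm may enrol patients at 3, 5 and 10 mg/kg, with 1 mg/kg for de-escalation. If a higher dose raises both ALC and the chance of response, patients with high or rising ALC will tend to be those given more ipilimumab. They would then respond more often even if ALC carried no information among patients on the same dose. The same reasoning extends to OS, because section 2.2.1 reports the best survival at 10 mg/kg in the melanoma studies.

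What is at stake is the reading of objective 1.3.1. An unadjusted association could not show whether ALC adds anything to knowing the assigned dose. No dosing decision and no primary or secondary result depends on it.

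**Working it through.** **1. The plan's own figures.** The best overall response rates in the three-dose melanoma study (section 2.2.1) were reproduced with exact 95% intervals, and all agree with the plan.

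| Dose (mg/kg) | Responders | Rate (95% CI) |
|---|---|---|
| 10 | 8/72 | 11.1% (4.9-20.7) |
| 3 | 3/72 | 4.2% (0.9-11.7) |
| 0.3 | 0/73 | 0% (0.0-4.9) |

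A Cochran-Armitage test for trend across the three doses gives p = 0.002. Within this trial's range the evidence is weaker. Fisher's test of 3 against 10 mg/kg gives p = 0.21. The post-transplant study, 0/6 against 7/22, gives p = 0.29.

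**2. Inputs for the confounding check.**
- N = 48, the maximum in section 13.2.
- Dose mixes at 3/5/10 mg/kg that fit section 5.3. Three cohorts of 6 plus a 6-patient expansion at 10 mg/kg give 6/6/12 per arm, so 12/12/24 in total. With 3, 3 and 6 patients and a 12-patient expansion at 10 mg/kg the total is 6/6/36. With the expansion at 5 mg/kg it is 12/24/12.
- Response by dose: 0/16/32% (ends from 0/6 and 7/22, midpoint assumed), or a milder assumed 15/22/32%.
- Share with high ALC by dose: assumed. Weak 0.3/0.4/0.5, moderate 0.3/0.5/0.7, strong 0.2/0.5/0.8. Only the direction comes from the documents.
- ALC and response independent within each dose, so the true within-dose odds ratio is 1.
- Two-sided 0.05. Section 13.5 says "All tests of treatment effects will be conducted at a 2-sided alpha level of 0.05, unless otherwise stated"; applying this level to the ALC tests is an assumption.

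**3. Expected pooled odds ratio.** With n_d patients, high-ALC share q_d and response r_d at dose d:

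- response in high ALC = Σ n_d q_d r_d / Σ n_d q_d
- response in low ALC = Σ n_d (1−q_d) r_d / Σ n_d (1−q_d)

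For mix 12/12/24, moderate shares and response 0/16/32%:

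- High ALC: 3.6 + 6 + 16.8 = 26.4 patients; 0 + 0.96 + 5.376 = 6.336 responders; 24.0%.
- Low ALC: 8.4 + 6 + 7.2 = 21.6 patients; 0 + 0.96 + 2.304 = 3.264 responders; 15.1%.
- Odds ratio = (0.240/0.760) / (0.151/0.849) = 1.77.

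**4. False-positive rate.** For each scenario 8,000 trials were simulated, comparing a pooled chi-square test with a dose-stratified Mantel-Haenszel test.

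| Mix | Response | ALC gradient | Pooled OR | Pooled test | Stratified test |
|---|---|---|---|---|---|
| 12/12/24 | 0/16/32% | weak | 1.32 | 7.2% | 4.8% |
| 12/12/24 | 0/16/32% | moderate | 1.77 | 10.6% | 4.6% |
| 12/12/24 | 0/16/32% | strong | 2.49 | 19.2% | 4.8% |
| 12/12/24 | 15/22/32% | strong | 1.48 | 8.3% | 4.9% |
| 6/6/36 | 0/16/32% | strong | 1.83 | 10.5% | 4.6% |
| 6/6/36 | 15/22/32% | weak | 1.09 | 5.4% | 4.9% |
| 12/24/12 | 0/16/32% | strong | 2.08 | 14.3% | 4.8% |
| 12/24/12 | 15/22/32% | weak | 1.11 | 5.3% | 4.9% |

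Over all 18 scenarios with both gradients (three mixes, three ALC gradients, two response gradients), the pooled test rejected in 5.3% to 19.2% of trials and the stratified test in 4.4% to 5.2%. The simulation error near 5% is √(0.05 × 0.95 / 8000) = 0.24 percentage points, so the lowest pooled rates cannot be told apart from 5%.

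**5. When there is no problem.** If ALC does not depend on dose, if response is flat across doses, or if all patients have one dose, the expected odds ratio is 1.00 and the pooled test stays near 5%. Only response was simulated; OS was not.

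**The case against.** Several objections are sound, and they limit the point.

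- **Pooling is not stated.** A reader might infer that the plan prescribes an analysis pooled over doses and arms. It does not; it is silent. If section 13.1's limits were meant to apply, each arm would contribute one dose and the problem would vanish. But section 13.1 does not mention ALC, and section 13.5 describes its population as recipients of the combination. The gap remains open.
- **The dichotomised level may be a baseline value.** Section 9.4 places baseline before dosing on cycle 1 day 1, when no ipilimumab has been given, so dose cannot have caused that level. This stands. The dose argument applies to on-treatment levels and to the change analysis.
- **The dose evidence is indirect.** It comes mainly from melanoma monotherapy, and the response trend leans partly on 0.3 mg/kg, which is not used here. Sections 2.5 and 9.4 warn that myelosuppression under decitabine may make ALC elevation unreliable. Zero response at 3 mg/kg is also too low an anchor: 0/6 has an exact 95% upper limit of 46%, and section 2.3 gives front-line decitabine CR rates of 18-25% in AML. The milder gradient is therefore shown as well.
- **Arm.** No section shows that ALC differs between the arms, so adjusting for arm is a precaution.
- **The analysis is exploratory, and strata would be sparse.** Both are true. Three doses by two arms make six strata for at most 48 patients, some with as few as three. This argues for a simple adjustment rather than full cross-stratification.

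A reader might also take section 2.2.1's caution, that earlier data could not separate an ipilimumab-specific link from a prognostic one, as support for this point. Adjusting for dose would not settle that question.

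**Conclusion.** The point holds in a limited form. Section 13.5 leaves out a factor that the plan's own background links to both ALC change and response. For on-treatment ALC and for the change to end of cycle 2, dose alone could produce or inflate an association.

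Under the assumed gradients, the expected pooled odds ratio is about 1.1 to 2.5 when the within-dose value is 1. The pooled false-positive rate for response is about 5% to 19%, against about 5% with dose stratification. The upper end needs the steepest assumed ALC gradient together with zero response at 3 mg/kg.

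It might be inferred that the ALC analysis is bound to return a spurious positive. The figures do not support that: even in the worst scenario about four trials in five would not reject. The effect is confined to interpretation of an exploratory biomarker, and correcting it is a cheap improvement.

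**What to change.** In section 13.5:

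1. State the time point of the dichotomised ALC.
2. For on-treatment ALC and for ALC change, report beside the pooled result an analysis adjusted for assigned dose level (one ordinal term, or stratification by dose) and arm. Use a Cox model or stratified log-rank test for OS, and Mantel-Haenszel or exact logistic regression for response.
3. Alternatively, restrict these analyses to RP2D patients within each arm and say so.

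An ALC level taken before the first ipilimumab dose does not need the dose adjustment on these grounds.

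The cost is a few sentences and no new data, since dose level and arm are assigned for every patient. The downside is some loss of precision among at most 48 patients, and fewer patients still under the RP2D restriction.
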